#### 9.7.1.1.3 EXPLORATORY ENDPOINTS

- Duration of response (DOR) by IIR and investigator assessment is defined as the time from the date a response was first documented until the date of the first documentation of PD or date of death from any case.
- Disease control rate (DCR) by IIR and investigator assessment is the proportion of subjects who have a best overall response of CR or PR or stable disease (SD). In this context, stable disease is defined as stable disease at  $\geq 7$  weeks after randomization to be considered best overall response.
- Clinical benefit rate (CBR) by IIR and investigator assessment is the proportion of subjects who have best overall response of CR or PR or durable SD (duration of SD  $\geq 23$  weeks after randomization).
- Efficacy endpoints (PFS, PFS-4m, PFS-1y, ORR-4m, and ORR) evaluated based on investigator assessment
- Proportion of subjects who achieve complete removal of baseline lesions and the proportion of subjects with unresectable baseline lesion(s) that are converted to resectable between the 2 treatment arms.
- Blood and tumor biomarkers will be assessed for identifying potential correlation with clinical outcomes-related endpoints.

#### 9.7.1.2 Definitions of Analysis Sets

The Full Analysis Set (Intent-to-Treat Analysis [ITT]) includes all randomized subjects regardless of the treatment actually received. This is the primary analysis population used for the efficacy analyses which will be based on the ITT principle.

The Per Protocol Analysis Set includes those subjects from the ITT set who received at least 1 dose of any study drug, had no major protocol deviations, and had both baseline and at least one postbaseline tumor assessment. Subjects for whom death occurred prior to the first postbaseline tumor assessment will also be included. The per protocol analysis set will be the secondary analysis set for efficacy endpoints.

The Safety Analysis Set includes subjects who received at least 1 dose of any study drug. This is the analysis population used for all safety analyses which will be based on as-treated principle.

Population Pharmacokinetic (PK) Analysis Set includes the subjects who have received at least 1 dose of lenvatinib with documented dosing history and have measurable plasma levels of lenvatinib.

The Pharmacodynamic Analysis Set includes subjects who received at least 1 dose of study drug and had sufficient pharmacodynamic data (eg, at least 1 evaluable/measurable pharmacodynamic parameter).

The HRQoL Analysis Set will consist of all randomized subjects who have received at least 1 dose of study medication, and have at least 1 patient-reported outcome (PRO) assessment completed beyond baseline. For PRO analysis, subjects will be analyzed as randomized and not according to treatment actually received.

#### 9.7.1.3      Subject Disposition

Reasons for screening failure will be summarized.

The number and percentage of subjects who completed the study will be summarized by treatment group, and for overall, and the number and percentage of subjects who discontinued prematurely will also be summarized by reason for discontinuation.

#### 9.7.1.4      Demographic and Other Baseline Characteristics

Demographic and other baseline characteristics for the Full Analysis Set will be summarized using descriptive statistics. Continuous demographic and baseline variables (including age, sex, race, height, and weight) will be summarized using n (number of subjects with available data), mean, standard deviation, median, quartiles 1 and 3, and range (minimum and maximum) unless otherwise specified. Categorical variables will be summarized by number and percentage.

#### 9.7.1.5      Prior and Concomitant Therapy

All investigator terms for medications recorded in the CRF will be coded to an 11-digit code using the World Health Organization Drug Dictionary (WHO DD). Concomitant medications will be further coded to the appropriate Anatomical Therapeutic Chemical (ATC) class indicating therapeutic classification. Prior medications will be defined as medications that started prior to the first dose of study drug and were either continued during the study or stopped prior to the first dose of study drug. Concomitant medications will be defined as medications that (1) started before the first dose of study drug and were continuing at the time of the first dose of study drug, or (2) started on or after the date of the first dose of study drug up to 30 days after the subject's last dose. All medications will be will be summarized and listed by drug and drug class and by treatment arm.

#### 9.7.1.6      Efficacy Analyses

Efficacy analyses will be based primarily on the Full Analysis Set.

All primary statistical analyses will be conducted at the data cutoff date for the primary analysis (ie, when approximately 38 PFS events, as determined by IIR, are observed).

#### 9.7.1.6.1 PRIMARY EFFICACY ANALYSIS

The primary efficacy endpoint of progression-free survival (PFS) per IIR will be analyzed and compared between the 2 treatment arms using the stratified log-rank test with time to first relapse/refractory disease (early [ $<18$  months] or late [ $\geq 18$  months]) and age ( $<18$  or  $\geq 18$  years) as strata. PFS censoring rules will follow FDA guidance of 2007 and will be detailed in the statistical analysis plan. Median PFS will be calculated using the K-M product-limit estimates for each treatment arm along with 2-sided 95% CIs (estimated with a generalized Brookmeyer and Crowley method [Brookmeyer and Crowley (1982)]). The K-M estimates of PFS will be plotted over time. The Cox regression model will be used to estimate the hazard ratio and its 95% CIs stratified by the stratification factors.

#### Secondary Efficacy Analyses

The PFS-4m rate and PFS-1y rate per IIR will be estimated using the K-M method for the primary efficacy endpoint PFS per IIR. PFS-4m/PFS-1y rate and their Greenwood standard errors will be evaluated using the K-M estimates from both treatment groups. The statistical significance of the difference in the 2 K-M PFS-4m rates will base on its 2-sided 95% CI. This 2-sided 95% CI and a p-value will be constructed using the difference of these 2 K-M PFS-4m/PFS-1y rates and the 2 corresponding Greenwood standard errors.

Overall survival (OS) will be compared between treatment arm and control arm following the same statistical method for the primary efficacy PFS endpoint. The K-M estimates will also be presented for 4, 6, 9, and 12 months (ie OS-1y) with 2-sided 95% CIs. OS-1y will be analyzed using the same approach as for the PFS-4m.

The ORR by IIR will be summarized and compared between the two treatment arms using stratified Miettinen and Nurminen's method. The difference in ORR and its 2-sided 95% confidence interval from the stratified Miettinen and Nurminen's method with strata weighting by sample size will be reported. The stratification factors used for randomization will be applied to the analysis. The ORR-4m by IIR will be summarized and compared between arms using the same approach as for ORR.

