### **Secondary Analyses**

The PFS-4m rate and PFS-1y rate will be estimated on the Full Analysis Set using the K-M method for the primary efficacy PFS analysis. PFS-4m/PFS-1y rate and their Greenwood standard errors will be evaluated using the K-M estimates from both treatment groups. The statistical significance of the difference in the 2 K-M PFS-4m rates will be based on its 2-sided 95% CI. This 2-sided 95% CI and a p-value will be constructed using the difference of these 2 K-M PFS-4m/PFS-1y rates and the 2 corresponding Greenwood standard errors.

Overall survival (OS) will be compared between treatment arm and control arm following the same statistical method for the primary efficacy PFS endpoint. Kaplan-Meier (K-M) estimates of OS rate will also be presented for 4, 6, 9, and 12 months with 2-sided 95% CIs.

The ORR will be summarized and compared between the two treatment arms using stratified Miettinen and Nurminen's method. The difference in ORR and its 2-sided 95% confidence interval from the stratified Miettinen and Nurminen's method with strata weighting by sample size will be reported. The stratification factors used for randomization will be applied to the analysis. The ORR-4m will be summarized and compared between arms using the same approach as for ORR.

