#### **Sample Size Rationale**

A total sample size of 72 subjects is estimated for the primary efficacy endpoint of PFS. Assuming a hazard ratio of 0.4 (median PFS of 3.5 and 8.75 months for the control arm and the test arm, respectively), a one-sided type 1 error rate of 0.025, and power of 80%, 38 PFS events are required for the primary analysis. The total sample size of 72 subjects is estimated to achieve 38 PFS events assuming the analysis occurs approximately 32 months after the first subject is randomized (assuming a 20-month enrollment period), and accounts for a dropout rate of up to 40%.

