#### 9.7.2 Determination of Sample Size

A total sample size of 72 subjects is estimated for the primary efficacy endpoint of PFS. A median PFS of 3.5 months for Arm B (control arm) has been estimated by comparing available PFS data from clinically active agents in this patient population ([Davis, et al., 2019](#); [Palmerini, et al, 2016](#); [Grignani, et al., 2012](#)). With respect to Arm A (lenvatinib plus chemotherapy arm), a median PFS of 8.75 months is estimated based on the results from Study 207.

Therefore, assuming a hazard ratio of 0.4, a 1-sided type 1 error rate of 0.025, and power of 80%, the required number of PFS events for the study is 38. The primary PFS analysis is estimated to occur at approximately 32 months after the first subject is randomized (assuming a 20-month enrollment period), and accounts for a dropout rate of up to 40%.

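### PFS-4m, and OS-1y by reference, can be declared statistically significant from its own 2-sided 95% CI whatever the primary PFS test shows

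*Protocol*

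**What the plan says.** The only type 1 error rate in the current protocol belongs to the primary endpoint. Section 9.7.2 gives "a 1-sided type 1 error rate of 0.025, and power of 80%, the required number of PFS events for the study is 38", and the synopsis (Sample Size Rationale) agrees: "a one-sided type 1 error rate of 0.025, and power of 80%, 38 PFS events are required for the primary analysis".

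For PFS-4m, the Secondary Efficacy Analyses under Section 9.7.1.6.1 state: "The statistical significance of the difference in the 2 K-M PFS-4m rates will base on its 2-sided 95% CI". The synopsis (Secondary Analyses) has: "The statistical significance of the difference in the 2 K-M PFS-4m rates will be based on its 2-sided 95% CI". The CI and a p-value come from the difference of the two Kaplan-Meier rates and their Greenwood standard errors. Neither place makes the rule depend on the primary result.

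The rule extends once by reference, in Section 9.7.1.6.1 only: "OS-1y will be analyzed using the same approach as for the PFS-4m". The synopsis gives OS rates with 95% CIs and no such sentence.

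The remaining secondaries have methods but no significance rule. PFS-1y has a CI and a p-value. OS is to be compared by the primary endpoint's method. ORR and ORR-4m are compared through a stratified difference with a 95% CI. No testing order, alpha split or nominal label appears in the current text, and Section 9.7.4 (other statistical issues) is marked not applicable. Section 9.7.1 leaves further detail to a SAP to be finalised before database lock.

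**The concern.** A 2-sided 95% CI lying wholly above zero is a one-sided 0.025 test in favour of lenvatinib. As written, PFS-4m therefore has a complete decision rule of its own that still operates when primary PFS has failed.

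PFS-4m is the endpoint where this matters most. It is one point on the curve that the primary log-rank test compares, and it was the primary endpoint until Amendment 02. If PFS just misses and the PFS-4m interval excludes zero, the protocol supports calling a PFS benefit statistically significant, although the 0.025 attached to the primary test does not protect that statement. OS-1y offers the same kind of free-standing claim for survival.

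**Working it through.** **1. The plan's own figure.** Inputs from Section 9.7.2: hazard ratio 3.5/8.75 = 0.4, one-sided 0.025, power 80%; allocation is 1:1. Schoenfeld's formula gives

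d = 4(z₀.₉₇₅ + z₀.₈₀)² / (ln 0.4)² = 4(1.960 + 0.842)² / 0.8396 = 37.4,

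rounded up to the stated 38. Power at 38 events is 80.6%. So 0.025 is the planning alpha, and it is the same level as one side of the 95% CI used for PFS-4m.

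**2. Multiplicity alone.** For two exact one-sided 0.025 tests with no true effect, P(either) = 0.025 + 0.025 − P(both). The correlation between the PFS and PFS-4m statistics was 0.75 to 0.80 in the simulations in step 3.

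| Correlation | P(both) | P(either) | P(PFS-4m only) |
|---|---|---|---|
| 0.75 | 0.0095 | 0.0405 | 0.0155 |
| 0.80 | 0.0110 | 0.0390 | 0.0140 |

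Independent tests would give 1 − 0.975² = 0.0494.

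**3. The tests as specified.** Simulation with 20,000 null trials per scenario, 36 per arm. PFS was tested by log-rank and PFS-4m by the Kaplan-Meier difference with Greenwood standard errors, each significant if z > 1.96.

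| Null scenario | PFS alone | PFS-4m alone | Either | PFS-4m but not PFS |
|---|---|---|---|---|
| Median 3.5 months, no dropout | 2.63% | 3.08% | 4.42% | 1.79% |
| Median 3.5 months, dropout | 2.58% | 2.98% | 4.17% | 1.59% |
| Median 6 months, dropout | 2.56% | 2.86% | 4.36% | 1.81% |

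A further check gave 4.3% to 4.6% for either and 1.6% to 1.7% for PFS-4m without PFS. The overall ranges are therefore 4.2% to 4.6% and 1.6% to 1.8%. With 20,000 trials, the Monte Carlo error on a rate near 4.4% is 1.96 × √(0.044 × 0.956/20,000), or about ±0.3 percentage points.

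**4. Splitting the excess.** Of the 4.2% to 4.6%, exact tests at the same correlation account for 3.9% to 4.0%. Most of the rest comes from the Greenwood interval, which rejects in 2.9% to 3.1% of null trials at this sample size instead of 2.5%. The primary test stays at about 2.6%.

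**5. Under the design alternative** (8.75 against 3.5 months), PFS-4m is significant with PFS not in 2.5% of trials.

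**Assumptions not in the documents.** Exponential PFS with a common median of 3.5 or 6 months under the null; uniform accrual over the 20 months; dropout of 40% per year, because the protocol gives up to 40% without a time scale; cutoff at the later of the 38th event and month 20, which gave on average 39 to 54 null events; no stratification; exact progression dates.

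**The case against.** The strongest reply is that testing hierarchies commonly sit in the SAP, which is not at hand, so a missing order here is no defect. That is right for an order that is merely absent. Here the protocol states, without condition, how PFS-4m significance is decided. A SAP that gated PFS-4m would have to narrow that sentence, so the protocol wording needs attention either way.

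A second reply is that these paragraphs describe methods, not claims. Section 9.7.1.6.2 applies the IIR approach to investigator-assessed PFS-4m, an exploratory endpoint, and nobody would read that as a formal test. This has some force for OS-1y, which is reached only through a reference to approach. It has less force for PFS-4m, where the sentence is expressly about statistical significance.

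Two stronger readings are tempting and should not be drawn. A reader might infer that the one-sided 0.025 is meant to cover every efficacy claim and has been breached. The protocol attaches it only to the primary PFS test, where it is valid. A reader might also count PFS, PFS-4m, PFS-1y, OS, OS-1y, ORR and ORR-4m as seven tests at full alpha and quote a joint error rate. The text does not support that. For OS it says only "Overall survival (OS) will be compared between treatment arm and control arm following the same statistical method for the primary efficacy PFS endpoint", which settles the method and sets no alpha. PFS-1y, ORR and ORR-4m have no decision rule, and a 95% CI is not in itself a significance claim.

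It is also fair that this is a Phase 2 trial with one clearly named primary endpoint.

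**Conclusion.** The point holds in a narrow form. PFS-4m, and OS-1y by reference in Section 9.7.1.6.1, can be called statistically significant whatever the primary PFS result.

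For PFS and PFS-4m together, the chance of a false claim in favour of lenvatinib is about 4.2% to 4.6%, or 1.7 to 1.8 times 2.5%. Multiplicity alone gives about 1.6 times. A PFS-4m claim beside a failed PFS occurs in about 1.6% to 1.8% of null trials. These sizes rest on the simulation assumptions listed above; that the joint rate exceeds 2.5% does not. No size is given for OS-1y, whose rule rests on the cross-reference.

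The primary analysis, its alpha, its power and the 38 events are unaffected. Severity is minor to moderate.

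**What to change.** In Section 9.7.1.6.1 and the synopsis (Secondary Analyses), do one of the following, with matching SAP wording:

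- **Gate it.** State that PFS-4m significance is assessed only if the primary PFS test is significant at one-sided 0.025, and put OS-1y under the same condition. If both are to be formal tests, state an order or split between them. The order of any further secondary tests is the sponsor's choice.
- **Or drop it.** Delete the significance sentence and state that all secondary CIs and p-values are nominal.

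Either change holds formal efficacy claims under the global null to the error of the primary PFS test. Gating does not cure the liberality of the Greenwood interval itself.

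The cost is wording only: 72 subjects, 38 events, the primary alpha and its power stay as they are. The downside is that PFS-4m or OS-1y cannot be called statistically significant if primary PFS fails. Under the design assumptions, that gives up a PFS-4m claim in about 2.5% of trials.

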#### 9.7.1.6.2 EXPLORATORY EFFICACY ANALYSES

Median DOR by IIR among responders for each arm will be presented along with its corresponding 2-sided 95% CIs. Disease Control Rate (DCR) and CBR by IIR will be summarized and compared between arms using the same approach as for ORR. Efficacy endpoints PFS, PFS-4m, PFS-1y, ORR-4m, ORR, DOR, DCR, and CBR evaluated based on investigator assessment will be analyzed using the same approach as for the endpoints assessed by IIR.

The difference in the proportion of subjects who achieve complete removal of baseline lesion(s) and the proportion of subjects with unresectable baseline lesions(s) that are

converted to resectable between the 2 treatment arms and corresponding two-sided 95% CIs will be calculated.

#### 9.7.1.7 Pharmacokinetic, Pharmacodynamic, and Other Biomarker Analyses

##### 9.7.1.7.1 PHARMACOKINETIC ANALYSES

Lenvatinib concentration versus time data will be tabulated and summarized and graphically presented.

Lenvatinib data from Arm A of the study will be pooled with available data from other studies and subjected to population PK analysis. The PK model will be parameterized in terms of clearance and volume of distribution. Details of the population PK analysis will be provided in a separate analysis plan.

##### 9.7.1.7.2 PHARMACODYNAMIC AND OTHER BIOMARKER ANALYSES

Pharmacodynamic, and other biomarker analyses may be performed and reported separately. Details of these analyses may be described in a separate analysis plan.

Optional pharmacodynamic serum and archived, fixed tumor tissue biomarkers may be collected from subjects in Arm A only as described in the Schedule of Assessments.

Pharmacodynamic serum and tumor biomarkers in this study will be identified as in other lenvatinib clinical studies.

Blood serum samples may be analyzed using global proteomic methods, enzyme-linked immunosorbent assay (ELISA), multiplex bead-based immunoassay, or other assays/methods and new technology in an effort to identify biomarkers.

Archived, fixed tumor tissue will be collected (if available) for assessment of mutations and other genetic alterations or proteins that may be important in the development and progression of cancer as well as for potential use in diagnostic development.

Data obtained from the pharmacodynamic samples will be used for research. The pharmacodynamic samples will not be used to determine or predict risks for diseases that an individual subject does not currently have. Any sample or derivatives (DNA, RNA, and protein) may be stored for up to 15 years to assist in any research scientific questions related to lenvatinib and for potential diagnostic development. If the subject reaches the age of 18 years (or at the appropriate age per local country requirements) while on the study, and becomes competent to give informed consent, his/her consent will be obtained using separate ICFs to continue on the study. Further analyses will not be performed on samples collected from subjects who do not reconsent at the age of 18 years (or at the appropriate age per local country requirements).

### 9.7.1.8 Safety Analyses

All safety analyses will be performed on the Safety Analysis Set. Safety data, presented by treatment group, will be summarized on an “as treated” basis using descriptive statistics (eg, n, mean, standard deviation, median, minimum, maximum for continuous variables; n [%] for categorical variables), as appropriate. Safety variables include TEAEs, clinical laboratory parameters, vital signs, 12-lead ECG results, Lansky play scores or Karnofsky performance scores, physical examination, height, tooth formation abnormalities, closure of proximal tibial plates, and LVEF. Study Day 1 for all safety analyses will be defined as the date of the first dose of study drug.

#### 9.7.1.8.1 EXTENT OF EXPOSURE

The number of cycles/days on treatment, quantity of study drug administered, dose intensity, and the number of subjects requiring dose reductions, treatment interruption, and treatment discontinuation due to adverse events will be summarized.

#### 9.7.1.8.2 ADVERSE EVENTS

The AE verbatim descriptions (investigator terms from the CRF) will be classified into standardized medical terminology using the Medical Dictionary for Regulatory Activities (MedDRA). Adverse events will be coded to the MedDRA (Version 20.1 or higher) lower level term (LLT) closest to the verbatim term. The linked MedDRA preferred term (PT) and primary system organ class (SOC) are also captured in the database.

A TEAE is defined as an AE that emerges during treatment (and within 30 days of the last study treatment), having been absent at pretreatment (Baseline) or

- Re-emerges during treatment, having been present at pretreatment (Baseline) but stopped before treatment,  
or
- Worsens in severity during treatment relative to the pretreatment state, when the AE is continuous.

Only those AEs that are treatment-emergent will be included in summary tables. All AEs, treatment-emergent or otherwise, will be presented in subject data listings.

The TEAEs will be summarized by treatment group. The incidence of TEAEs will be reported as the number (percentage) of subjects with TEAEs by SOC and PT. A subject will be counted only once within an SOC and PT, even if the subject experienced more than 1 TEAE within a specific SOC and PT. The number (percentage) of subjects with TEAEs will also be summarized by highest CTCAE grade.

The number (percentage) of subjects with TEAEs will also be summarized by relationship to study drug (Yes [related] and No [not related]).

The number (percentage) of subjects with treatment-related TEAEs will be summarized by SOC and PT. Treatment-related TEAEs include those events considered by the investigator to be related to study treatment. The number (percentage) of subjects with treatment-related TEAEs will also be summarized by highest CTCAE grade.

Adverse events will be summarized using the Safety Analysis Set. The number of AEs and number and incidence (%) of subjects with AEs will be summarized by treatment group and overall. To obtain the incidence (%), the number of subjects with at least 1 event and the percentage of subjects with AEs by SOC and by PT will be calculated. Incidence (%) by causal relationship with study drug and by severity (CTCAE v5.0) will also be calculated. For clinically significant events, time of onset, and recovery will be reported.

Adverse events will be summarized for descriptive purposes by age (2 to <6, 6 to <18, and  $\geq 18$ ), and sex.

The number (percentage) of subjects with TEAEs leading to death will be summarized by MedDRA SOC and PT for each treatment group. A subject data listing of all AEs leading to death will be provided. All deaths will also be summarized.

The number (percentage) of subjects with treatment-emergent SAEs will be summarized by MedDRA SOC and PT for each treatment group. A subject data listing of all SAEs will be provided.

The number (percentage) of subjects with TEAEs leading to discontinuation from study drug will be summarized by MedDRA SOC and PT for each treatment group. A subject data listing of all AEs leading to discontinuation from study drug will be provided.

